1.4.5 Schedule of Visits and Procedures

—

Evaluation	Screening Baseline	Daily	Stu (idy T every	End of Study Treatment ^o				
		a		15	30	45	60	75	(± 2 days)
Fatty acid profile and Holman Index ^g		х		x	x	х	х	x	х
Genetic polymorphism sample (buccal swab) ^h		х							
Phytosterol, cholesterol, and squalene levels ⁱ		х		x	x	x	х	x	х
Human chorionic gonadotropin (hCG) ^j	X								
	١	Nutritional I	ntake						
PN lipid intake ^k		х	X	X	X	Х	Х	Х	Х
Other macronutrient PN intake		х	x	x	x	x	х	x	х
Breast milk intake ¹	X	X	X	X	X	X	Х	X	Х
Enteral formula intake	X	Х	X	X	X	Х	Х	Х	Х
Oral food intake	Х	Х	X	х	х	Х	Х	х	Х
Concomitant medications / nutritional supplements ^m	х	х	x	x	x	x	х	x	х
Concomitant procedures	X	X	X	X	X	X	Х	X	Х
Adverse events ⁿ	X	X	X	X	X	X	Х	X	Х

PN=parenteral nutrition

^a Baseline evaluations should be done \leq 24 hours before first study treatment administration, however, baseline laboratory assessments may be done within \pm 24 hours of first study treatment administration. Baseline tests need not be repeated if within 24 hours of screening sampling. Buccal swabs can be collected at any time before the end of study treatment.

^b Randomization is recommended within 24 hours of signing consent but must occur within 3 days of signing consent (protocol section 7.1)

^c For all neonates (premature infants born <37 weeks of gestation up to 1 month CA and full-term neonates <1 month of age), gestational age (GA) will be recorded at Screening and categorized as full-term (born \geq 37 weeks of gestation), preterm (32-36 weeks of gestation), very preterm (28-31 weeks of gestation), or extremely preterm (<28 weeks of gestation).

^d Including weight and length or height (and head circumference for infants <1 year of age). For all neonates (premature infants born <37 weeks of gestation up to 1 month CA and full-term neonates <1

Evaluation	Screening	Baseline	Daily	Stu (ıdy T every	reatn 715 d days)	nent I ays ±)	Day 2	End of Study Treatment ^o
		a		15	30	45	60	75	(± 2 days)

month of age), BW will be recorded at Screening and categorized as normal BW (≥2500 g), low BW (1500-2499 g), very low BW (1000-1499 g), or extremely low BW (<1000 g).

^e Vital signs will be collected once daily at approximately the same time each day (e.g. 8 AM), with a window of approximately 2-3 hours. Vital signs include heart rate (beats/min), respiratory rate (breaths/min), systolic and diastolic blood pressure (mmHg), and body temperature (°C).

^f Diagnosis of neonatal morbidities diagnoses including BPD, ROP, IVH, PVL, NEC, and late-onset sepsis in enrolled premature and low birth weight neonates. Diagnostic criteria and severity grading will be per standard-of-care.

^g Samples are to be collected \geq 4 hours after completing last lipid infusion. Samples are to be collected at the same time every day.

^h Buccal swab samples for the determination of genetic polymorphisms for FADS1 (rs174553) and FADS2 (rs174575, rs99780, rs174583) will be collected after enrollment in all patients for whom consent is obtained. Buccal swabs can be collected at any time before the end of study treatment. Buccal swabs will be destroyed once all analyses have been completed.

ⁱ Clarification on laboratory measurements will be provided in a separate laboratory manual.

^j All female patients \geq 12 years of age must have a negative urine human chorionic gonadotropin (hCG) pregnancy test at screening. For female patients <12 years of age, a urine hCG test at screening will be performed at the discretion of the investigator based on childbearing potential.

^k Parenteral nutrition therapy may be interrupted and restarted (based on the initial randomization) within a 1 to 2-day window, subject to adjudication from the medical monitor who conducts clinical review of current patient status, assessment of any potential AE/SAEs, discussion/clarification with investigator to resume or abort study treatment. If there is a likelihood that the patient will require restart of PN within 1 to 2 days of the initial stoppage, then it is recommended to delay performing the End of Study Treatment procedures. However, the End of Study Treatment procedures should be completed within 2 days of the initial stoppage if the patient has not restarted PN.

¹When breastfeeding intakes cannot be measured, the best estimation (volume) of the investigator will be recorded.

^m Medications and nutrition supplements received within 30 days prior to randomization by the patient and the nursing mother (if applicable) also will be recorded at Screening. The nursing mother's medication history will be collected from the patient's chart (if available).

ⁿ Adverse events occurring prior to the initiation of the first study procedure will be recorded as signs and symptoms in the patient's medical history. During the course of the study, and for 30 days after the last dose of study drug, the Investigator or designee will routinely monitor and solicit each patient for the occurrence of any AEs. All SAEs or any pregnancy reports with or without an associated SAE must be reported to Baxter Global Pharmacovigilance within 24 hours of site's knowledge of the event.

° End of study treatment is defined as the last day of PN with Intralipid or Clinolipid; maximum 90 days of study treatment is allowed. After 90 days, the patient will receive nutritional intervention as prescribed by their healthcare provider if still required.

1.5 Analysis Populations

Three main analysis sets are defined for this study.

1.5.1 Definition of Analysis Populations

Full analysis set (FAS): all patients who are randomized to receive either Clinolipid or standard of care soybean oil-based lipid emulsion (Intralipid) and have received at least one randomized study treatment. This dataset will follow the intent-to-treat principle and will analyze patients by planned randomized arm.

Per protocol set (PPS): all patients in the FAS who have Holman Index measurements taken at baseline and at least 1 other timepoint post-baseline, who have received a minimum of 7 days of ILE treatment, and are without a major protocol violation (i.e. violation that potentially impacts the primary endpoint).

Deviations that could be considered for exclusion in a PP analysis

- Randomization or treatment errors
- Investigational product not handled properly
- Key exclusion criteria such as:
 - Patients with liver disease including cholestasis
 - Patients with severe hyperlipidemia or severe disorders of lipid metabolism
 - Patients who are unable to tolerate necessary laboratory monitoring
 - Patient requires or is expected to require propofol for sedation

Deviations that should **not** lead to exclusion of data in a PP analysis

- Patients who violate inclusion/exclusion criteria relating to patient safety
- Missed informed consent signature/date
- Any deviation that does not directly impact the primary endpoint

Safety analysis set (SS): the set of all patients who have been administered study treatment (Clinolipid or Intralipid). Patients will be analyzed according to treatment received.

1.5.2 Protocol Deviations

Protocol deviations will be summarized for all patients in the FAS pooled together. Patient counts will be presented for minor protocol deviations, major protocol deviations, and for each category of major protocol deviation.

Protocol deviations will also be listed for the FAS. The listing will include patient id, age, randomized treatment, verbatim description of the protocol deviation, the assigned category of protocol deviation, major/minor status and whether the protocol deviation was determined to be exclusionary for PPS.

1.6 Endpoints

1.6.1 Primary Endpoint

• Risk of EFAD. EFAD will be defined using the Holman Index value of >0.4.

Supportive of the primary endpoint

- Time to developing EFAD
- The Holman Index
- Fatty acid (FA) profiles
- Genetic polymorphisms in FADS1 and FADS2 genes

1.6.2 Secondary Endpoints

The secondary objectives in patients receiving either Clinolipid or Intralipid are to evaluate:

- The risk of developing liver disease including PNALD:
 - PNALD will be defined by direct bilirubin ≥2 mg/dL when no other etiology for liver dysfunction is present;
 - Hepatic integrity will be assessed by measuring plasma liver function tests: alkaline phosphatase (ALP), aspartate aminotransferase (AST), alanine aminotransferase (ALT), gamma-glutamyl transferase (GGT), and total and direct bilirubin;
 - Plasma main phytosterols (stigmasterol, campesterol, sitosterol), cholesterol and squalene levels will be assessed. Phytosterols levels will be correlated with the risk of developing PNALD.
- The adequacy of nutritional interventions:

- Prescribed and actual nutritional intakes (energy, protein, carbohydrates, and lipid) from both PN and enteral/oral nutrition will be collected and recorded on a daily basis and summarized on a daily basis during the first 2 weeks of treatment and on an approximately 15-day basis afterwards up to the end of study treatment in each of the treatment groups.
- Growth will be assessed and evaluated from baseline to end of study treatment on an approximately every 15-day basis using descriptive summary statistics for weight, and height/length (and head circumference in infant <1 year) in each of the treatment groups as follows:
 - Gain in weight (g/kg/day in infants <1 year of age, g/day in children and adolescents) and gain in length/height (mm/week in all) and head circumference (mm/week in infants <1 year);
 - Changes in the standard deviation score (SDS or z-score) from reference growth curves (Fenton growth curve for premature infants, World Health Organization (WHO) growth standards for infants and children ages 0 to 2 years, or Center for Disease Control (CDC) growth charts for children age ≥2 years).
- The safety profiles as evaluated by:
 - Adverse events (AEs)
 - Serious adverse events (SAEs)
 - Adverse events of special interest (AESIs)
 - AESIs are known AEs related to PN with ILEs, per Intralipid and Clinolipid United States Prescribing Information (USPI) and include the following: catheter related infection, thrombophlebitis; EFAD as well as ILE-related Immediate or Early adverse reactions including: dyspnea, cyanosis, allergic reactions, hyperlipemia, hypercoagulability, nausea, vomiting, headache, flushing, increase in temperature, sweating, sleepiness, pain in the chest and back, slight pressure over the eyes, dizziness, irritation at the site of infusion, and ILE-related delayed adverse reactions including: hepatomegaly, jaundice, splenomegaly, thrombocytopenia, leukopenia, transient increases in liver function tests, and overloading syndrome (focal seizures, fever, leukocytosis, hepatomegaly, splenomegaly and shock).

- Vital signs
- Laboratory tests (see Table 1 below)
- Additional neonatal morbidities including bronchopulmonary dysplasia (BPD), retinopathy of prematurity (ROP), intraventricular hemorrhage (IVH), periventricular leukomalacia (PVL), necrotizing enterocolitis (NEC), and lateonset sepsis in enrolled premature infants born <37 weeks of gestation up to 1 month corrected age (CA)

Hematology:	Liver function tests:
Hematocrit (Hct)	Alkaline phosphatase (ALP)
• Hemoglobin (Hgb)	• Alanine aminotransferase (ALT; SGPT)
Mean corpuscular hemoglobin (MCH)	Aspartate aminotransferase (AST; SGOT)
Mean corpuscular hemoglobin concentration	Gamma-glutamyl transferase (GGT)
(MCHC)	Total bilirubin
Mean corpuscular volume (MCV)	Direct bilirubin
Platelet count	Serum Chemistry:
Mean Platelet Volume (MPV)	• Glucose
Red blood cell (RBC) count	Triglycerides
• White blood cell (WBC) count with	• Serum Albumin
differential	• Creatinine
	• Blood urea nitrogen (BUN)
• Urine human chorionic gonadotropin (hCG) ^a	Bicarbonate (CO2)
	• Sodium (Na)
	• Potassium (K)
	Chloride (Cl)
	• Calcium (Ca)
	• Phosphorus (P)
	• Magnesium (Mg)

Table 1. List of Local Laboratory Tests

^a All female patients ≥12 years of age must have a negative urine human chorionic gonadotropin (hCG) pregnancy test at screening. For female patients <12 years of age, a urine hCG test at screening will be performed at the discretion of the investigator based on childbearing potential.

1.7 Interim Analysis

An interim analysis has not been planned for this study.

2. ANALYSIS METHODS

2.1 General Principles

Unless otherwise specified, summary statistics (n, mean, standard deviation [SD], median, minimum, and maximum values) will be presented for continuous variables. Counts and, if relevant, percentages will be presented for categorical variables.

Unless otherwise specified, data listings will include patient ID, treatment group, sex, age at screening (given in months) and baseline weight.

Unless otherwise noted, all analyses will be performed using SAS/Graph® 9.4 software, SAS/STAT® 15.1 software, and Base SAS® 9.4. Copyright © 2016, SAS Institute Inc. SAS and all other SAS Institute Inc. product or service names are registered trademarks or trademarks of SAS Institute Inc., Cary, NC, USA. All Rights Reserved

Except for height, weight, head circumference, or otherwise specified, the estimated mean, Q1, median, and Q3 for a set of values will be displayed to 1 more significant digit than the original values, standard deviations will be displayed to 2 more significant digits, and minimum and maximum values will be displayed with the same number of significant digits as the original values. If an original value has more than 2 decimal places, the significant digits will be counted as if there are 2 decimal places. All percentages will be displayed with 1 decimal place unless more decimal places are needed to show 1 significant digit (i.e. a percentage of 0.01 will be shown as 0.01 as opposed to 0.0). For height, weight, and head circumference, up to 4 reported decimals are shown.

Unless otherwise specified, age group will be defined and stratified as follows: Pre-Term Neonate (24 weeks to <37 weeks), Full Term Neonate (\geq 37 weeks to <1 month), Infant (\geq 1 month to <12 months), Child (\geq 1 year to <10 years), and Adolescent (\geq 10 years to <18 years)

Unless otherwise specified, weight at birth will be grouped as follows: Normal (\geq 2500 g), Low (1500-2499 g), Very Low (1000-1499 g), and Extremely Low (<1000 g).

2.1.1 Definition of baseline

Unless otherwise specified, baseline is defined as the values collected at the baseline visit. The value closest to the start of treatment will be used for baseline if multiple values (e.g. laboratory re-tests) are available. If the value at baseline is missing, then the value at the screening visit will be used as baseline.

Any medical condition that is present at the time that a participant is screened will be considered baseline medical history and will not be reported as an adverse event.

Change from baseline variables will be calculated as the post-treatment value minus the value at baseline.

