6.4 Physical Examination

Physical examinations will be conducted as per the SOC for the study site and documented for the study at Screening, Baseline and approximately every 15 days up to end of study treatment. In particular, clinical signs of EFAD (flaky dry skin, hair loss, hair depigmentation, poor wound healing, increased susceptibility to infections, growth status) will be considered as well as liver diseases specific symptoms (e.g. jaundice, hepatomegaly).

Any clinically significant (CS) new abnormal condition or worsening of a preexisting condition from Screening will be recorded in the CRF as AE.

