6.13 Adverse Events Assessments

An AE is any untoward medical occurrence in a patient or clinical investigational patient administered a study product, and that does not necessarily have a causal relationship with the treatment or drug. An AE can therefore be any unfavorable and unintended sign (including an abnormal laboratory function), symptom (e.g., rash, pain, discomfort, fever, dizziness, etc.), organ dysfunction (e.g., cardiovascular failure, pancreatitis, etc.), systemic illness (e.g., sepsis), or outcome of death temporally associated with the use of the study product, whether or not the event is considered associated with the study product.

Laboratory and vital sign abnormalities qualify as AEs if medical intervention is required to treat or address the abnormality, if the patient must be discontinued from the study due to the abnormality, or if the value exceeds specific limits defined by the SOC as qualifying it as an AE.

An elective procedure/surgery that occurs during the course of a study, but is being performed for a documented pre-existing condition and was pre-planned prior to study entry, will not qualify as an AE. If, however, the pre-existing condition unexpectedly deteriorates during the study requiring the procedure/surgery to be performed earlier than

planned, the condition for which the procedure/surgery is being performed will qualify as an AE.

In this study, AEs will be recorded in conjunction with the first study procedure (Screening). Adverse events occurring prior to the initiation of the first study procedure will be recorded as signs and symptoms in the patient's medical history. Adverse events occurring during Screening but prior to the administration of study treatment will be considered as unrelated to study treatment.

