7.1 Screening Period

After providing written IC, patients will enter the Screening Period. The Screening Period is defined as the period after the ICF is signed and dated until randomization. The maximum duration of this period is 3 days prior to dosing. Randomization is recommended within 24 hours of signing consent but must occur within 3 days of signing consent. If patient is not randomized within 24 hours of informed consent, patient should be started on SOC ILE on Day 1 of PN as per Table 4 and Section 5.3. Signing and dating of the ICF and the Screening visit may occur on the same day, if necessary; however, the ICF must be signed and dated before any Screening activities can be conducted.

The aim of the Screening Period is to determine the eligibility (inclusion/exclusion criteria) of patients for randomization.

Further assessments conducted during Screening include:

- Demographics
- Gestational age and birth weight for infants <1 years of age only
- Medical history (including diagnosis requiring PN)
- Physical examination, including weight and length or height (and head circumference for infants <1 year of age)
- Vital signs
- Laboratory evaluations including hematology and chemistry (refer to Appendix 1, Schedule of Events Table)
- Pregnancy test. Note: All female patients ≥12 years of age must have a negative urine human chorionic gonadotropin (hCG) pregnancy test at screening. For female patients <12 years of age, a urine hCG test at screening will be performed at the discretion of the investigator based on childbearing potential.
- Nutritional intakes
- Medication history
- Randomization to study treatment
- Adverse Events (AEs occurring during Screening but prior to administration of study treatment will be considered as unrelated to study treatment). Non-serious AEs during this time period will be collected as part of the medical history. Serious adverse events will need to be reported as per Section 6.13.7.2.

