2.5.1 Adverse Events

2.5.1.1 Derivation of Adverse Events

Adverse events (AEs) will be coded using MedDRA. They will be classified as follows:

Pre-treatment adverse event – An adverse event that starts between the date of signing the informed consent form (ICF) and the study treatment

Treatment-emergent adverse event (TEAE) – An adverse event that starts on or after the start of study treatment

Treatment-emergent adverse events of special interest (AESI) - The following are called out as AESIs in the protocol: catheter related infection, thrombophlebitis, dyspnea, cyanosis, allergic reactions, hyperlipemia, hypercoagulability, nausea, vomiting, headache, flushing, increase in temperature, sweating, sleepiness, pain in the chest and back, slight pressure over the eyes, dizziness, irritation at the site of infusion, hepatomegaly, splenomegaly, thrombocytopenia, leukopenia, and overloading syndrome (focal seizures, fever, leukocytosis, hepatomegaly, splenomegaly and shock). A blinded review of AEs will be conducted at the end of the study before unblinding to flag AESIs.

An adverse event will be considered related to study treatment if they respond 'Probably related' or 'Possibly related' to relationship to study treatment.

In case of incomplete information on study treatment or AE onset, events will be classified as treatment-emergent unless there is sufficient data to rule out the possibility that the event started after the start of study treatment.

If the severity of an adverse event is missing, then that adverse event will be classified as *severe*. If relationship of an adverse event is missing, then that adverse event will be classified as *probably related*.

The number of events per 100 patient days will be calculated as follows:

$$\frac{\text{Number of Total Events}}{\sum_{i=1}^{n} (\text{End Date of Treatment}_{i} - \text{Start Date of Treatment}_{i} + 1)}, \\100$$

where i represents each patient and n represents the total number of patients in the Safety Set for that treatment group.

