2.5.1.2 Analysis of Adverse Events

An AE overview summary table will be prepared to include the number of patients, the percentage of patients (%), and the number of events per 100 patient days by treatment group, for the following categories:

- 1. Any AE
- 2. Any treatment-emergent adverse event (TEAEs)

- 3. Treatment emergent non-serious AEs
- 4. Treatment-emergent serious AEs (SAEs)
- 5. Treatment-emergent AEs of special interest (AESIs)
- 6. Treatment-emergent AEs related to study treatment
- 7. Treatment-emergent SAEs related to study treatment
- 8. Treatment-emergent AEs leading to death

Additional listings and tables on the above categories (with the exception of #1) will be given by SOC and PT. Pre-treatment adverse events (those occurring between informed consent and treatment) will also be listed. For SAE listings, the seriousness criteria will be included in the listing.

The tables below will display the total number of patients, the percentage of patients (%), the number of events, the number of events per 100 patient days, system organ class (SOC), and preferred term by treatment group. Table summaries will be produced for:

- Treatment-emergent AEs by severity
- Treatment-emergent SAEs by severity
- Treatment-emergent AEs by relationship to study treatment
- Treatment-emergent SAEs by relationship to study treatment
- Treatment-emergent adverse events in ≥5% of patients (in either Clinolipid or Intralipid group)

Tables by preferred term and tables by system organ class (SOC) and preferred term will be sorted in descending order by the percentage of patients.

Adverse event listings will be sorted by patient ID and adverse event start date. They will include primary AE number, SOC, PT, verbatim term, adverse event start and end date and its duration, treatment date, relationship to study treatment, alternate causality, severity, action taken, seriousness, outcome, whether the event is ongoing, and whether AE led to discontinuation from study.

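### Neither the SAP nor the protocol has a worsening clause in its treatment-emergent definition, and SAP 2.1.1 conflicts with the protocol on pre-existing conditions, so on-treatment worsening can be left out of the treatment-emergent AE tables

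*SAP*

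**What the plan says.** SAP 2.1.1, which defines baseline, also contains a rule on adverse events. A condition already there when the participant is screened "will be considered baseline medical history and will not be reported as an adverse event". Nothing is said about a condition that later gets worse.

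SAP 2.5.1.1 then classifies events by start date. A treatment-emergent event is "An adverse event that starts on or after the start of study treatment". A pre-treatment event is "An adverse event that starts between the date of signing the informed consent form (ICF) and the study treatment". Where the onset or treatment information is incomplete, "events will be classified as treatment-emergent unless there is sufficient data to rule out the possibility" that it began after dosing. SAP 2.5.1.2 adds: "Pre-treatment adverse events (those occurring between informed consent and treatment) will also be listed". Its tables by system organ class and preferred term cover the treatment-emergent categories. The category of any AE appears only in the overview table.

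The protocol takes a different line on worsening:

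- Section 6.4, on clinically significant findings at physical examination: "worsening of a preexisting condition from Screening will be recorded in the CRF as AE".
- Section 6.7.1 asks the investigator whether an abnormal laboratory value is a new or a worsening event.
- Section 6.13 counts a pre-existing condition as an AE if it deteriorates unexpectedly and brings a planned procedure forward.

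Protocol 6.13.8 defines treatment-emergent by occurrence after treatment has begun and, like the SAP, has no worsening clause. On screening-period events, Protocol 6.13 has AEs recorded from the first study procedure, whereas Protocol 7.1 says: "Non-serious AEs during this time period will be collected as part of the medical history". SAP section 3 declares no change from the protocol's analyses.

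**The concern.** Safety is a secondary objective, and these patients have active disease at entry: Protocol 6.3 lists sepsis and necrotizing enterocolitis among the diagnoses that call for parenteral nutrition. Under Protocol 5.3 and 7.1, standard-of-care lipid may be running before screening or during the screening period of up to 3 days. Some events of special interest, such as thrombocytopenia, raised temperature or catheter-related infection, could already be present at that point. Triglycerides exclude a patient only above 400 mg/dL.

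In such patients an effect of the study lipid could show as deterioration of something already there. If the plan has no agreed way to count that, the answer depends on which passage a site or a programmer happens to follow, and the treatment-emergent tables may be incomplete in a way that the reader cannot see.

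**Working it through.** No figure in the plan bears on this point, so there is nothing to reproduce. The check is to follow a worsening through the rules under each way it could be recorded.

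| How the worsening is recorded | Rule that applies | Result |
|---|---|---|
| Condition in medical history; the site opens a new AE dated at the worsening (Protocol 6.4) | SAP 2.5.1.1: start date is after dosing | Treatment-emergent, counted |
| Condition in medical history; SAP 2.1.1 taken literally | No AE is reported | Not counted |
| AE opens between consent and dosing; one record keeps its first start date; it worsens after the first dose | SAP 2.5.1.1: start date is before dosing | Pre-treatment: listed, plus the any-AE overview row |
| Non-serious screening event placed in medical history (Protocol 7.1), then worsens on treatment | Either of the first two rows; it is unclear whether SAP 2.1.1 reaches an event arising after the screening visit | Depends on site and programmer |

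Three steps follow from the third row.

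1. The default to treatment-emergent does not rescue the event, because that default applies only when dates are incomplete. Here the onset is known.
2. The event is missing from the treatment-emergent table, and so also from the related-event and special-interest tables, which are subsets of it.
3. Protocol 6.13 deems events before dosing unrelated to study treatment. A record that keeps its screening onset may carry that attribution forward.

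For the size, let N be the number of on-treatment AEs when each worsening counts once, w the share of N that are worsenings of earlier conditions, and p the fraction of those worsenings that do not get their own on-treatment date. Then

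reported count = N − p·w·N = N(1 − p·w).

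- If every worsening is entered as a new AE (p = 0), the count is N and the loss is 0.
- If none is (p = 1), the count is N(1 − w) and the loss is the fraction w.

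The denominator of the rate per 100 patient days is built from treatment start and end dates, so it does not change, and the rate falls by the same fraction p·w. The documents give neither p nor w.

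**The case against.** The strongest reply is that nothing in the plan actually removes a worsening. SAP 2.1.1 sits under the definition of baseline and can be read as describing a condition as it stood at screening. The protocol tells investigators to record worsening, and Protocol 6.13.1 captures an onset date and severity for each event. A worsening entered that way is treatment-emergent. The SAP has no step that deletes AEs matching medical history.

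This stands, and it defeats a stronger conclusion that a reader might draw: that all on-treatment worsening drops out of the safety tables and that the loss is complete. The documents support only that it can be left out. The objection does not close the gap, because no passage tells sites to open a new record when an existing one worsens, and SAP 2.1.1 read literally tells them not to report.

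Two other tempting inferences also fail. The start-date rule is not a departure by the SAP, since Protocol 6.13.8 lacks a worsening clause too. Nor do serious screening events vanish: Protocol 7.1 exempts them from the medical-history route, Protocol 6.13.7.2 requires every SAE from consent to 30 days after the last dose to be reported, and the SAP plans a listing of serious pre-treatment events.

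Finally, platelets, triglycerides and temperature have change-from-baseline summaries, and liver tests have shift tables as well. That is a partial backstop. These tables carry no severity grade, seriousness or causality. Results from unscheduled visits are kept out of table summaries (SAP 2.1.2), missing laboratory data are expected (SAP 2.5.2.4), and physical examinations are listed only (SAP 2.5.2.8). Catheter-related infection depends on the AE record.

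**Conclusion.** The point holds as a conflict and a gap. SAP 2.1.1 contradicts Protocol 6.4, 6.7.1 and 6.13 on worsening; both treatment-emergent definitions omit it; and Protocol 7.1 contradicts 6.13 and the SAP on non-serious screening events. On-treatment worsening of a pre-existing or screening-onset condition can therefore be absent from the treatment-emergent, related and special-interest tables. For an event opened before dosing and kept as a single record, that absence follows directly from the stated rules. For a condition held as medical history, it depends on how the site records the worsening.

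The undercount is between 0 and w. It cannot be narrowed without the share of on-treatment events that are worsenings and knowledge of site practice.

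This should be fixed but is not critical. The study is descriptive, with no hypothesis tests, and the primary endpoint comes from the Holman Index, which this does not touch.

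**What to change.** 1. In SAP 2.1.1, add after the rule: *unless it worsens in severity, frequency or seriousness on or after the first study dose, in which case the worsening is an AE with onset on the date of worsening*.
2. In both SAP 2.5.1.1 and Protocol 6.13.8, define a treatment-emergent AE as one that starts, or worsens in severity or seriousness, on or after the first dose. The protocol describes no severity grade for medical history, so a programmed comparison is not possible there; for those conditions rely on the investigator's new AE record dated at the worsening.
3. Reconcile Protocol 7.1 with Protocol 6.13 and the SAP, so that non-serious screening-period events are recorded in one way, as pre-treatment AEs.

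Make the change before unblinding, so that the counting rule is not chosen with results in view. The cost is the wording in both documents, a clarification to sites, one extra severity comparison in the AE programming, and slightly higher treatment-emergent counts.
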